1.1 Primary Objectives

- Determine the Dose limiting toxicity (DLT) of fractionated dose of ¹⁷⁷Lu-PSMA-617
- Determine the cumulative maximum tolerated dose (MTD) and/or recommended phase II dose (RP2D) of ¹⁷⁷Lu-PSMA-617 in a 2-week dose-fractionation regimen

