Cohort	Treatment Dose mCi (GBq)		Total mCi (Dose GBq)	Subjects (n)
	Day 1	Day 15			
-1	50 (1.85)	50 (1.85)	100 (3.7)	1-6
1	100 (3.7)	100 (3.7)	200 (7.4)	1-6
2	150 (5.55)	150 (5.55)	300 (11.1)	1-6
3	200 (7.4)	200 (7.4)	400 (14.8)	3-6
4	250 (9.25)	250 (9.25)	500 (18.5)	3-6
5	300 (11.1)	300 (11.1)	600 (22.2)	3-6

4.2 Rationale for Dose-Escalation Strategy:

This study will use a modified phase I 3+3 dose-escalation study design, with the planned initial and subsequent cohorts described in Table 7. This study design is well-described and accepted by the clinical and scientific community, so we will not provide complete details here. Briefly, this design is constructed to reduce the chance of escalating the dose when the probability of DLT is high, and increase the chance of escalating the dose when the probability of DLT is low. Given the fact that some pre-existing clinical efficacy and toxicity data exists with the study drug, we will allow up to 6 subjects to be treated at a given dose-level even in the absence of DLT. The MTD is defined as the highest dose level with an observed incidence of DLT in no more than one out of six patients treated at a particular dose level. The dose escalation scheme provides the following probabilities of escalation based on the true chances of DLT at a specific dose level. One can see that the probability of escalation is high if the toxicity risks are low:

True Probability of Toxicity:	.05	.10	.20	.30	.40	.50	.60
Probability of Escalation:	.97	.91	.71	.49	.31	.17	.08

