6.1.2. Treatment Phase

The treatment and early monitoring phase comprises of 8 visits spanning over approximately 12 weeks.

Platelets, absolute neutrophil count, bilirubin, transaminases, and serum creatinine must be performed with results available and within range of eligibility criteria within 1 week prior to treatment initiation on C1D1.

Details for each visit are listed below:

6.1.2.1 ^{177}Lu -PSMA-617 infusion (Treatment Visit 1 Day 1)

The following procedures must be completed on the day of treatment with ^{177}Lu -PSMA-617:

- Targeted Physical Examination with vital signs and weight
- Medical History
- Brief Pain Inventory, FACT-P
- ECOG Performance Status
- CBC with differential and platelet count
- CMP (with direct bilirubin with known Gilbert's syndrome)
- PSA
- LDH
- Single intravenous dose of ^{177}Lu -PSMA-617 (Dose based on the Cohort in which the subject is enrolled)
- Adverse event evaluation
- Concomitant medications
- Concomitant procedures

As stated above, platelets, absolute neutrophil count, bilirubin, transaminases, and

renal function assessment must be available within 1 week prior to treatment on D1 and meet eligibility criteria.

For Treatment Visit 2 (**Day 15 ±1 day**), grade ≥ 2 thrombocytopenia or neutropenia within 24 hours of the second dose of ^{177}Lu -PSMA-617 requires a subject's treatment to be held until the toxicity has resolved to least grade 1. If the toxicity has not resolved after 2 weeks of monitoring, the subject's ^{177}Lu -PSMA-617 treatment will be permanently discontinued and will be termed dose-limiting toxicity

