6.2.9. Imaging Plan

A. ^{68}Ga -PSMA-HBED-CC PET/CT Scan

Patient preparation should be according to the policies and procedures of the local imaging site (CIBC). The patient does not need to be fasting for either the infusion or

the scans. The use of intravenous or oral contrast will not be permitted. Specifications for acquiring the ⁶⁸Ga-PSMA-HBED-CC PET/CT scans will be provided in study specific documentation by the study chair or the co-investigators from the Division of Nuclear Medicine. PET/CT should be obtained during the Screening Visit as well as at the end of study visit. The images are acquired between 1 and 3 hours after the ⁶⁸Ga-PSMA-HBED-CC infusion. Image acquisition will be from vertex of skull to mid thighs.

B. ¹⁷⁷Lu-PSMA-617 Planar/SPECT imaging

Patient preparation should be according to the policies and procedures of the local imaging site (CIBC). The patient does not need to be fasting for either the infusion or the scans. The use of intravenous or oral contrast will not be permitted. Specifications for acquiring the ¹⁷⁷Lu-PSMA-617 planar/SPECT images will be provided in study specific documentation by the study chair or the co-investigators from the Division of Nuclear Medicine. Planar/SPECT images should be obtained during the Imaging Visit (Day 8 ±1) on all subjects after the ¹⁷⁷Lu-PSMA-617 infusion. Image acquisition will be from vertex of skull to mid thighs. Optional images will be performed on selected consenting subjects between initial Treatment Visit (between D1 - D4) and prior to Treatment Visit 2 (Day 15 ±1).

Managing toxicity

NCI CTCAE version 4.0 is used to grade all adverse events.

- Grade ≥ 2 thrombocytopenia or neutropenia within 24 hours of the second dose of ¹⁷⁷Lu-PSMA-617 (Treatment Visit 2) requires a subject's treatment to be held until the toxicity has resolved to least grade 1. If the toxicity has not resolved after 2 weeks of monitoring, the subject's ¹⁷⁷Lu-PSMA-617 treatment will be permanently discontinued and will be termed dose-limiting toxicity.

Dose-limiting toxicity (DLT) is defined as:

- Grade 4 hematologic toxicity that is deemed at least possibly related to ¹⁷⁷Lu-PSMA-617 will be termed dose-limiting toxicity.
- Any grade > 2 non-hematologic toxicity deemed to be at least possibly related to ¹⁷⁷Lu-PSMA-617 will require a subject's ¹⁷⁷Lu-PSMA-617 treatment to be permanently discontinued and will be termed dose-limiting toxicity.

Maximum Tolerated Dose (MTD) is defined as:

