6.4. Duration of Therapy and Criteria for Removal from Study

Duration of treatment portion of the study (excluding screening time) will be approximately 85 Days (± 7 days). By signing the informed consent form and agreeing to participate in this study, the subjects are required to participate in entirety up to the completion of all scheduled visits and study procedures, or until one of the following criteria applies:

- A protocol violation occurs
- Disease progression occurs
- A serious or intolerable adverse event occurs (that in the opinion of the Investigator, requires the subject's discontinuation)
- The Investigator withdraws the subject (at the Investigator's discretion for reasons other than the adverse event)
- The Principle Investigator terminates the protocol
- The subject requests to be discontinued from the protocol
- The subject is lost to follow-up
- Intercurrent illness that prevents administration of ⁶⁸Ga-PSMA-HBED-CC or ¹⁷⁷Lu- PSMA-617
- Previous anaphylactic reaction to PSMA peptides/ligands

The investigators or physicians may stop the protocol or terminate a subject's participation in the protocol at any time should they judge:

- That it is not in the subject's best interest to continue
- If the subject experiences a protocol-related injury
- If the subject needs life-saving medications/procedures/treatment
- If the subject does not comply with the study plan
- General or specific changes in the patient's condition render the patient unacceptable for further treatment in the judgment of the investigator

They may also remove the subject from the study for various other administrative and medical reasons. They can do this without the patient's consent.

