12.5. Analysis of Endpoints

12.5.1. Analysis of Primary Endpoints

The primary endpoint will be the proportion of subjects with DLT from Treatment Visit 1 through **Efficacy/Scan Visit**. The MTD is the highest dose amongst the different dose-level cohorts in this study at which no more than 2 (33%) of the subjects in a cohort experience DLT.

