12.7. Reporting and Exclusions

12.7.1. Evaluation of toxicity

All subjects will be evaluable for toxicity from the time of their first infusion with ⁶⁸Ga-PSMA-HBED-CC as well as when they receive their first treatment with ¹⁷⁷Lu-PSMA-617. The distributions of the maximum observed grade toxicity will be tabulated for each type of toxicity and presented by dose level and overall. Results will be summarized with descriptive statistics.

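### Phase I defines no DLT-evaluable set or replacement rule, so subjects lost early for non-DLT reasons can count as DLT-free and push the cumulative MTD upward

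*Combined protocol and SAP*

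**What the plan says.** - **Target.** Section 1.1 seeks the MTD and/or recommended phase II dose as a cumulative dose. Under Section 4.1 that is two infusions two weeks apart.
- **Endpoint.** Section 12.5.1: "The primary endpoint will be the proportion of subjects with DLT from Treatment Visit 1 through" the Efficacy/Scan Visit, which Table 8 places at Day 85 ± 7. The denominator is not defined further.
- **Toxicity population.** Section 12.7.1: "All subjects will be evaluable for toxicity from the time of their first infusion". No minimum exposure or follow-up is required. The section then describes tabulating the maximum grade of each toxicity by dose level and overall.
- **Ways out before Day 85.** Section 6.4 includes "Disease progression occurs", and also withdrawal, loss to follow-up, intercurrent illness, an intolerable adverse event and investigator discretion.
- **Missed second doses that are DLTs.** Section 6.1.2, on grade 2 or higher neutropenia or thrombocytopenia not resolved after two weeks: "treatment will be permanently discontinued and will be termed dose-limiting toxicity". The Managing toxicity text under Section 6.2.9 repeats this and applies the same label to related non-hematologic toxicity above grade 2: "treatment to be permanently discontinued and will be termed dose-limiting toxicity".
- **Escalation rule.** Section 4.2: "The MTD is defined as the highest dose level with an observed incidence of DLT in no more than one out of six patients". Sections 4.2 and 12.1 tabulate the resulting escalation probabilities.
- **Other evaluable sets.** Sections 4.2 and 12.2 define one for phase II. Section 12.7.2 defines one for response and has the only wording on replacement. Neither covers phase I DLT.

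**The concern.** A 3+3 decision rests on three to six subjects, so how one incomplete subject is counted can change it. The quantity of interest is the DLT risk of the full two-infusion dose over about 12 weeks. A subject who had one infusion, or a few weeks of follow-up, and left without a DLT tells us little about that risk. If he is counted as a completed DLT-free observation, the observed rate is too low and escalation past a toxic level becomes more likely. All subjects enter with progressive metastatic disease, so some early exits for progression are plausible. Some losses may also be informative. Non-hematologic DLT requires a grade above 2, so a subject who stops after dose 1 for an intolerable grade 2 non-hematologic toxicity is not a DLT and never receives the cumulative dose.

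**Working it through.** **1. The plan's own figures.** Let p be the true DLT rate and q = 1 − p. A level is passed with 0 of 3 DLTs, or with 1 of 3 followed by 0 of 3:

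P(escalate) = q³ + 3pq² × q³ = q³ + 3pq⁵.

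For p = 0.05, 0.10, 0.20, 0.30, 0.40, 0.50, 0.60 this gives 0.973, 0.906, 0.709, 0.494, 0.309, 0.172, 0.082. The table in Sections 4.2 and 12.1 (0.97, 0.91, 0.71, 0.49, 0.31, 0.17, 0.08) is reproduced. The formula treats every subject as fully observed and uses the limit of at most 1 of 6.

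**2. Early non-DLT losses counted as DLT-free.** Let d be the share of subjects who are incomplete and k the share of their full-dose DLT risk that is still observed. Neither is in the documents; both are assumptions. The apparent rate is

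p_e = p(1 − d) + kpd = p[1 − d(1 − k)],

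which goes into the same formula. At p = 0.40:

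| d | k | p_e | P(escalate) |
|---|---|---|---|
| 0 | – | 0.40 | 0.2160 + 0.0933 = 0.309 |
| 10% | 0.5 | 0.38 | 0.2383 + 0.1044 = 0.343 |
| 20% | 0.5 | 0.36 | 0.2621 + 0.1160 = 0.378 |
| 10% | 0 | 0.36 | 0.378 |
| 20% | 0 | 0.32 | 0.3144 + 0.1396 = 0.454 |

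With d = 20%, from k = 0.5 to k = 0, the probability moves from 0.709 to 0.752-0.793 at p = 0.20, from 0.494 to 0.557-0.622 at p = 0.30, and from 0.172 to 0.234-0.309 at p = 0.50.

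**3. One subject.** If exactly one of the first three is unobserved and counted DLT-free,

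P(escalate) = q² + 2pq × q³.

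At p = 0.30 this is 0.49 + 0.42 × 0.343 = 0.634, against 0.494. At p = 0.40 it is 0.36 + 0.48 × 0.216 = 0.464, against 0.309.

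**4. Across levels.** Take illustrative true rates of 0.05, 0.10, 0.20, 0.30 and 0.45 at Cohorts 1 to 5, ignoring Cohort -1. The chance of clearing all five is the product of the escalation probabilities:
- no loss: 0.973 × 0.906 × 0.709 × 0.494 × 0.234 = 0.07
- d = 10%, k = 0: 0.978 × 0.922 × 0.752 × 0.557 × 0.301 = 0.11
- d = 20%, k = 0: 0.983 × 0.937 × 0.793 × 0.622 × 0.378 = 0.17

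**5. The remedy.** Suppose the DLT-evaluable set is any subject with a DLT plus those with full exposure and follow-up. With k = 0 and non-informative loss, the evaluable-set rate is p and the stated table is restored. With k above 0 the set is slightly conservative. At p = 0.40, d = 20%, k = 0.5, DLTs make up 0.8 × 0.40 + 0.2 × 0.20 = 0.36 of all subjects and the evaluable set 0.80 + 0.04 = 0.84. The rate is 0.36/0.84 = 0.43 and P(escalate) is about 0.26, against the intended 0.31.

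**The case against.** Several stronger readings are tempting, and the documents do not support them.

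- **That every one-infusion subject counts as DLT-free.** Unresolved hematologic toxicity at dose 2 and related non-hematologic toxicity above grade 2 are themselves termed DLTs. Only other losses are at issue.
- **That the plan instructs DLT-free scoring.** It does not. Section 12.7.1 reads as an ordinary all-treated safety population for toxicity tables. The scoring follows from applying the only toxicity-evaluability rule to the proportion in Section 12.5.1. That is a literal reading, but an inference.
- **That subjects who receive only the diagnostic tracer dilute the DLT rate.** Section 12.7.1 mentions the tracer, but the endpoint window opens at Treatment Visit 1.
- **That the bias is known to be large.** No loss rate is given, and k = 0 is extreme, since every incomplete subject has had at least one infusion. Blood counts are scheduled on Days 8, 15, 22 and 29. The progression visit (Section 6.1.5) includes laboratory tests and adverse event evaluation, and Sections 6.5 and 13.3 continue follow-up of adverse events.

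There are also partial safeguards: safety review before each escalation (Section 12.6), notice to the DSMB after each completed cohort (Section 14), and the option of six subjects per level without a DLT (Section 4.2). They may dilute the effect, but none says how an incomplete subject is counted, and a completed cohort is not defined. Section 6.2.4 already gives 600 mCi as the phase 2 total, the top level in Table 7. This suggests, without stating it, that escalation may be over. A replacement rule would then have little left to act on, but the reported DLT proportion would still need a denominator.

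**Conclusion.** The concern holds for subjects who miss the second infusion or leave before Day 85 for reasons that are not DLTs: progression, withdrawal, loss to follow-up, intercurrent illness, or toxicity below the DLT threshold. Applied literally, Sections 12.7.1 and 12.5.1 keep them in the denominator as DLT-free, and the cumulative MTD is biased upward. The direction follows whenever such losses are counted this way and some of their risk goes unobserved. The size is conditional. At a true DLT rate of 40%, under the at-most-1-of-6 limit, P(escalate) goes from 0.31 to 0.34-0.38 with 10-20% loss and half the risk still observed, and to 0.38-0.45 with none observed. These loss rates are assumptions, and nothing in the documents shows that the selected dose was in fact affected.

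**What to change.** 1. Keep all treated subjects in the adverse event tables of Section 12.7.1.
2. In Section 12.5.1, define a DLT-evaluable set for escalation and MTD decisions: any subject with a DLT in the window, plus subjects who received both infusions and were followed through the Efficacy/Scan Visit.
3. Replace other subjects where the six-per-level ceiling leaves room, and say what is done where it does not.
4. Report the DLT proportion on both denominators, all treated and DLT-evaluable, noting that the second is slightly conservative. If escalation is finished, this reporting step still applies.
5. Reconcile the MTD limits: at most one of six (Sections 4.2 and 12.1), no more than 2 or 33% (Section 12.5.1), and the level at which more than two of six have a DLT (Managing toxicity, under Section 6.2.9). Likewise reconcile footnote c of Table 8, which discontinues the second dose without calling it a DLT, with Section 6.1.2 and Managing toxicity, which do.

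The cost is a short definition, an occasional replacement with some delay, and a slightly conservative DLT rate. No spare place remains once a level has six subjects.

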
¹⁷⁷ Lu-PSMA I&T	22	3.4 – 7.4	1-4	0	0	Heck et al 2016
¹⁷⁷ Lu-PSMA-617	43	6	1-4	0	0	Zimbelmann et al 2016
¹⁷⁷ Lu-PSMA-617	5	5.8 – 7.4	1	0	0	Chakraborty et al 2016

*One patient had pre-treatment baseline platelet count of grade 4

NR = not reported

A dose fractionated regimen provides the theoretic benefit of higher cumulative radiation dose to the target tissue/organ while limiting toxicities secondary to non-specific binding of the radiolabeled ligand. In addition to the toxicity data provide above, our group has consistently seen evidence of dose-response (see Table below), justifying a dose-escalation study.

Group	N	Any PSA decline	≥30% PSA decline	> 50% PSA decline	Median OS mo [95% CI]*
Total	49	55.1%	32.7%	16.3%	22.9 [16.2, 29.7]
Low doses	16	37.5%	12.5%	6.3%	14.6 [9.9, 19.4]
RP2D	33	66.7%	42.4%	21.2%	27.7 [15.8, 39.6]
40 x2 cohort	16	50.0%	25.0%	12.5%	19.6 [9.1, 30.2]
45 x2 cohort	17	87.5%	58.8%	29.4%	48.3 [16.0, 80.6]

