3.2. Inclusion Criteria

1. Histologically or cytologically confirmed adenocarcinoma of prostate
2. Documented progressive metastatic CRPC based on Prostate Cancer Working Group 3 (PCWG3) criteria, which includes at least one of the following criteria:
 - PSA progression
 - Objective radiographic progression in soft tissue
 - New bone lesions
3. ECOG performance status of 0-2
4. Have serum testosterone < 50 ng/dL. Subjects must continue primary androgen deprivation with an LHRH/GnRH analogue (agonist/antagonist) if they have not undergone orchiectomy.
5. Have previously been treated with at least one of the following in any disease state:
 - Androgen receptor signaling inhibitor (such as enzalutamide)
 - CYP 17 inhibitor (such as abiraterone acetate)
6. Have previously received taxane chemotherapy (in any disease state), been determined to be ineligible for taxane chemotherapy by their physician, or refused taxane chemotherapy.
7. Age ≥ 18 years

8. Patients must have normal organ and marrow function as defined below:

○ Absolute neutrophil count○ Hemoglobin○ Platelet count○ Serum creatinine○ Serum total bilirubin○ Serum AST and ALT	
$\geq 2,000 \text{ cells/mm}^3$ $\geq 9 \text{ g/dL}$ $\geq 150,000 \times 10^9/\mu\text{L}$ $\leq 1.5 \times \text{upper limit of normal (ULN)}$ or calculated creatinine clearance $\geq 60 \text{ mL/min}/1.73 \text{ m}^2$ by Cockcroft-Gault $\leq 1.5 \times \text{ULN}$ (unless due to Gilbert's syndrome in which case direct bilirubin must be normal $\leq 3 \times \text{ULN}$ in absence of liver metastases; $< 5 \times \text{ULN}$ if due to liver metastases (in both circumstances bilirubin must meet entry criteria)

--	---
9. Ability to understand and the willingness to sign a written informed consent document.

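### The toxicity table in Section 12.7.1 ignores baseline grade, so unchanged laboratory abnormalities admitted at entry can be counted as toxicity of a 177Lu dose level

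*Combined protocol and SAP*

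**What the plan says.** Section 12.7.1 gives the tabulation rule: "The distributions of the maximum observed grade toxicity will be tabulated for each type of toxicity and presented by dose level and overall". It adds only that results will be summarized descriptively. The same section opens the window before any 177Lu is given: "All subjects will be evaluable for toxicity from the time of their first infusion with" the 68Ga agent, as well as at the first 177Lu treatment.

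Inclusion criterion 8 (Section 3.2) is introduced with "Patients must have normal organ and marrow function as defined below", but its limits reach beyond normal:

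- AST and ALT: up to 3 x ULN "in absence of liver metastases", and below 5 x ULN "if due to liver metastases (in both circumstances bilirubin must meet entry criteria").
- Bilirubin: up to 1.5 x ULN, "unless due to Gilbert's syndrome in which case direct bilirubin must be normal".
- Creatinine: up to 1.5 x ULN, "or calculated creatinine clearance" of at least 60, an alternative that leaves creatinine itself uncapped.
- Hemoglobin: 9 g/dL or above.

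In its review of prior data, the protocol does take baseline into account. The footnote to Table 6 (Section 2.5) explains a zero count for grade 4 platelets: "One patient had pre-treatment baseline platelet count of grade 4".

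**The concern.** A maximum grade per patient says how bad a value became, not whether it changed. A patient who enters with raised transaminases and stays there has the same maximum grade as one who reaches that level after treatment. Likewise, a patient who enters at one grade and remains there cannot be told from a patient who worsens into it.

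The affected items are among the risks that the protocol itself names: anemia, transaminase elevation and renal failure in Section 2.6, and renal insufficiency and hepatic enzyme elevation in Section 13.1.1. Safety by CTCAE 4.0 and the correlation of toxicity with radiation dosimetry are secondary objectives (Section 1.2). Phase I dose levels hold at most six subjects (Table 7). At that size, one or two patients with pre-existing abnormality can create or mask an apparent dose-toxicity pattern in the descriptive tables.

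**Working it through.** The plan states no figure on this point, so there is none to reproduce. The check is mainly one of text, followed by arithmetic on scale.

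**1. Does any other section supply a baseline rule?**

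- Section 13.1 defines an adverse event by temporal association with drug use, without a causality judgment and without a new-or-worsened condition.
- Section 13.1.2 defines attribution categories, and the unrelated category covers the patient's clinical state. Section 12.7.1 does not use attribution.
- Section 13.1.3 has all adverse events logged.
- Section 12.1 adds only generic descriptive statistics.

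None of these refers to baseline grade, shift or worsening.

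**2. Can an eligible patient be abnormal before 177Lu?** Yes for AST/ALT, bilirubin and creatinine, because the limits are multiples of the upper limit of normal. For hemoglobin the documents give no lower limit of normal; that 9 g/dL lies below it is an assumption. The CTCAE 4.0 cut-points are not reproduced, so the documents show abnormality at entry but not the exact baseline grade.

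**3. Is a baseline value available?** Yes. CBC and CMP are collected at screening and on Day 1 (Table 8, Sections 6.1.1 and 6.1.2.1). Section 6.1.2 also requires neutrophils, platelets, bilirubin, transaminases and creatinine within one week before Day 1. Hemoglobin is not in that list but is part of the CBC.

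**4. Weight of one patient.** 1/6 = 16.7%, or 17 points, in a full phase I cohort; 1/3 = 33 points in a cohort of three; 1/27 = 3.7 points if the recommended dose level reaches 27 subjects.

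**5. Illustration with no drug effect.** Let b be the share entering with a given abnormality that persists and is logged. The documents do not give b, so the range is assumed. The chance that a dose level of n subjects shows at least one case is 1 - (1 - b)^n.

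| b (assumed) | n = 3 | n = 6 |
|---|---|---|
| 5% | 0.143 | 0.265 |
| 10% | 0.271 | 0.469 |
| 20% | 0.488 | 0.738 |
| 30% | 0.657 | 0.882 |

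For example, 1 - 0.9^6 = 0.469. If only grades above the pre-infusion grade are counted, the figure under the same no-effect assumption is 0.

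**6. Illustration with a drug effect.** With new-onset rate r among patients normal at entry, the tabulated rate is b + (1 - b)r. The any-grade rates in the German retrospective series (Section 2.3.1) are AST 19%, renal failure 12% and ALT 8%. Treating them as new-onset rates is a second assumption.

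| b (assumed) | AST | Renal failure | ALT |
|---|---|---|---|
| 10% | 27.1% | 20.8% | 17.2% |
| 20% | 35.2% | 29.6% | 26.4% |

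For ALT at b = 10%: 0.10 + 0.90 x 0.08 = 0.172. Over b = 5% to 30%, ALT runs from 12.6% to 35.6%.

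**The case against.** The strongest reply is that the plan tabulates toxicity, not raw laboratory grades. An investigator may regard a value unchanged since before dosing as no adverse event, or call it unrelated. Table 8 starts adverse event monitoring at Treatment Visit 1, and the screening list in Section 6.1.1 has no adverse event evaluation. This stands in part. A reader might infer that pre-existing abnormality will be reported as toxicity; the documents support only that it can be, because no text either requires or forbids it.

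The evaluability sentence can also be read as two starting points, one per agent. Nothing expressly assigns events after 68Ga alone to a 177Lu dose level. That reading is fair, but the table is broken down only by dose level and overall, and the start differs from Table 8, so the counting rule is unsettled.

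A reader might also infer that this is the only planned safety summary, or that the MTD is at risk. Neither is supported. Section 12.5.1 analyses the proportion with DLT, Section 12.6 plans real-time safety analyses before each escalation, and Section 14 gives the DSMB an adverse event table. DLT requires grade 4 hematologic or grade above 2 non-hematologic toxicity at least possibly related to study agent, with attribution reviewed by the study chair (Section 6.2, toxicity management). Protection is large rather than complete: the Section 4.1 trigger for opening cohort -1 refers to any grade 3 or higher toxicity without stating relatedness. Whether an eligible entry value could reach that grade depends on cut-points not in the documents.

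Finally, the illustrated rates are not evidence. The baseline share is assumed, one value is applied to items with different entry limits, and the chart-review rates may already include baseline abnormality, in which case the sum double-counts. This objection stands in full.

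**Conclusion.** The point holds for the descriptive safety tables. Section 12.7.1 sets a maximum-grade rule with no baseline reference, no other section supplies one, and eligibility admits above-normal liver and renal values and hemoglobin down to 9 g/dL. Unchanged pre-existing abnormality can therefore be counted as toxicity of a dose level.

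The firm measure of size is the weight of one patient: 17 points in a cohort of six. The statement that a reported ALT rate would more than double (8% to 17%) should not be read as a finding; it needs an assumed 10% baseline share, full persistence and logging, and chart-review rates taken as new-onset. Neutrophils and platelets are much less exposed, since their entry limits (2,000 cells/mm³ and a platelet limit of 150,000) are stricter. No conclusion about the DLT rate or the MTD follows. This is an improvement available at almost no cost, not an error that invalidates the plan.

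**What to change.** In Section 12.7.1:

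1. Keep the maximum-grade table for all events, by dose level and overall.
2. For laboratory items, also tabulate the worst grade after the first 177Lu infusion that exceeds the last grade before that infusion.
3. Add a shift table of baseline grade by worst post-infusion grade, by dose level, for hemoglobin, creatinine, AST/ALT and bilirubin. Neutrophils and platelets are optional.
4. List events between the 68Ga infusion and the first 177Lu infusion separately, not under a 177Lu dose level.
5. Reconcile the start of evaluability in Section 12.7.1 with the start of adverse event monitoring in Table 8.

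The cost is analysis wording and a few extra tables. The screening, Day 1 and follow-up CBC and CMP results are already in the schedule, so no visit, sample or patient is added.
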